12.3. Assessments of Neurological Function

Because opioid drugs may produce adverse effects on the CNS, subjects will be monitored for the appearance of CNS symptoms not only at the time of scheduled vital sign assessments, but as needed throughout the study duration. Level of sedation will be assessed according to SOC at each Institution. Examples include the Ramsay Sedation Scale and the University of Michigan Sedation Scale (see [Appendix A](#)). If sedation is determined to be clinically significant, it should be recorded as an AE.

12.4. Pharmacokinetic Assessments

12.4.1. Blood Sample Collections

Blood collection may be performed using an existing line (arterial or venous noted on eCRF) at the start of the study (the use of EMLA[®] at the insertion site is permitted). If access for blood sampling is lost, a new line will only be established as part of the clinical management of the subject; otherwise, the subject's participation in the study will be early terminated. Procedures for blood draws should follow institutional SOC. All catheter lines should be appropriately flushed per institutional SOC prior to each blood draws. The discard volume must be restricted to 0.5 mL for tubing with a dead space of ≤ 0.5 mL and up to 1.0 mL for tubing with a dead space > 0.5 mL. Calculation and evaluation of the following pharmacokinetic variables will be performed for all subjects participating in study: (Single-Dose Phase: C_{max} , T_{max} , AUC_{0-t} , AUC_{0-24} , $AUC_{0-\infty}$, λ_n , $t_{1/2}$, CL/F [clearance], and V/F [volume of distribution]; Multiple-Dose Phase: C_{max} , T_{max} , AUC_{0-t} , λ_n , $t_{1/2}$, and CL/F; see [Table 7](#) for definitions). Blood samples (0.5 mL) will be obtained and placed into 2.0-mL dipotassium ethylenediaminetetraacetic acid (K₂EDTA) tubes at each blood collection time point for both phases (see [Table 3](#) and [Table 4](#)). The samples will be obtained at the following times:

- Single-Dose Phase: Serial blood will be collected at time 0 (Baseline), at 15 and 30 minutes, and at 1, 1.5, 2, 4, 6, 8, 12, and 24 hours post dose.
- Multiple-Dose Phase: Serial blood will be collected at: 0 (Baseline), at 0.5, 1, 1.5, and 2 hrs post-Dose 1, immediately prior to Doses 2, 3, 4, 5, 6, 7, and at 0.5, 1, 1.5, and 2 hrs post Dose 7.

Table 7: Pharmacokinetic Variables

Variable	Definition
C_{\max}	Maximum plasma concentration; the highest concentration observed during a dosage interval
T_{\max}	The time at which C_{\max} was observed
AUC_{0-t}	Area under the concentration versus time curve from time 0 to the last measured concentration (C_t) in the dosing interval, calculated by linear trapezoidal rule
$AUC_{0-\infty}$	Area under the concentration versus time curve from time 0 to infinity, calculated as $AUC_{0-t} + C_t/\lambda_n$
AUC_{0-24}	Area under the concentration versus time curve from time 0 to 24 hours (end of dosing interval)
λ_n	Terminal rate constant, calculated as the negative slope of the ln-linear portion of the terminal plasma concentration-time curve
$t_{1/2}$	Terminal half-life, calculated as $\lambda_n/(\ln 2)$
CL/F	Apparent oral clearance, calculated as Dose/ $AUC_{0-\text{inf}}$ for single dose or Dose/ $AUC(0-\tau)$ for steady-state
V/F	Apparent volume of distribution, calculated as Dose/ $(AUC_{0-\text{inf}} * \lambda_n)$

Immediately after collection, the tube will be gently inverted several times to mix the anticoagulant with the blood sample. The plasma fraction will be separated by placing the collection tube into a refrigerated centrifuge (4°C to 8°C) for 10 minutes at 1,500 × g. The plasma fraction will be withdrawn by pipette and placed into a polypropylene freezing tube in 1 aliquot for subjects with body weights 3 to 6 kg and in 2 approximately equal aliquots for subjects with body weights greater than 6 kg. All sample collection and freezing tubes will be clearly labeled in a manner that identifies the subject and the collection time. Labels will be fixed to the freezing tubes in a manner that will prevent the label from becoming detached after freezing. All plasma samples will be placed into a freezer at –70°C or below within 1 hour after collection. The additional blood draws for the purposes of pharmacokinetic assessment in this study do not pose more than a minor risk to the subjects.

Total blood volume that will be collected for research purposes, including any discard volume, will be based on the age and weight criteria in section 12.4.2.

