
Name of Sponsor/Company: Endo Pharmaceuticals Inc.
Name of Investigational Product: EN3319 Oxymorphone HCl Immediate-Release Oral Liquid
Name of Active Ingredient: Oxymorphone HCl
Investigational Product, Dosage and Mode of Administration: Single-Dose Phase; EN3319 Oxymorphone HCl Immediate-Release Oral Liquid 1 mg/mL dosed at 0.05 mg/kg, 0.10 mg/kg, and 0.15 or 0.20 mg/kg (or a different dose [not to exceed 0.30 mg/kg] as determined by the IDMC) by mouth. Multiple-Dose Phase; up to 3 dose levels of EN3319 Oxymorphone HCl Immediate-Release Oral Liquid 1 mg/mL based on the recommendation of the IDMC.
Duration of Study: Screening Phase – up to 21 days Single-Dose Phase – 1 day Multiple-Dose Phase – 2 days Follow-up telephone call – 14 days
Reference Therapy, Dosage and Mode of Administration: Not applicable
Criteria for Evaluation: Effectiveness: For subjects aged 6 to ≤ 12 years, assessment of current pain intensity will be obtained using the FPS-R for 12 hours (Single-Dose Phase) or 48-hours (Multiple-Dose Phase) following dose administration, or until rescue medication is used in accordance with the Schedule of Study Assessments/Procedures (see Table 3 and Table 4). For subjects aged 2 to < 6 years, assessment of current pain intensity will be obtained using the FLACC behavioral measurement for up to 12 hours (Single-Dose Phase) or up to 48-hours (Multiple-Dose Phase) following dose administration, or until rescue medication is administered in accordance with the Schedule of Study Assessments/Procedures (see Table 3 and Table 4). Pharmacokinetics: Single-Dose Phase: determination of C_{max} , T_{max} , C_{12} , AUC_{0-t} , AUC_{0-24} , $AUC_{0-\infty}$, λ_n , $t_{1/2}$, CL/F (clearance) and V/F (volume of distribution); Multiple-Dose Phase: determination of C_{max} , T_{max} , AUC_{0-t} , λ_n , $t_{1/2}$, CL/F, and V/F. Safety and Tolerability: Safety will be assessed using adverse events (AEs), assessments of respiratory and neurological function, vital signs, urine drug screen, and clinical laboratory tests. Assessment of safety and tolerability will also include a pharmacokinetic assessment. Blood samples for pharmacokinetic assessments of oxymorphone HCl immediate-release oral liquid will be obtained over a 24-hour period (Single-Dose Phase) or over a 48-hour period (Multiple-Dose Phase) following oxymorphone HCl immediate-release oral liquid administration.

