6. OBJECTIVES

6.1. Primary Objective

The primary objective of the Single-Dose and Multiple-Dose Phase is to characterize the effectiveness, safety, and tolerability of oxymorphone HCl immediate-release oral liquid in children aged 2 to ≤ 12 years requiring an opioid to treat their acute postoperative pain of various etiologies.

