NOTE: Within each age group, dose assignment will begin at lowest single dose and will proceed to the next dose after completion of all subjects. During the Single-Dose Phase, if rescue is needed, all study procedures (including PK) will continue except collection of pain scores. PK will only be discontinued if rescue is via oxycodone or oxymorphone. Within each age group, the Multiple-Dose Phase may proceed after IDMC assessment of the Single-Dose Phase data and selection by the IDMC of the treatment cohort doses that will be used in the Multiple-Dose Phase.

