7.1.4. Single-Dose Phase Assessments and Procedures

The following assessments and procedures will be performed during the Single-Dose Phase (see [Table 3](#)) after the baseline assessments have been completed and the subject is dosed. Every effort should be made to collect blood samples at the assigned time intervals relative to the time of administration of study drug:

- Assess and record current pain intensity at 15 and 30 minutes and at 1, 1.5, 2, 4, 6, 8, 12, and 24 hours (or upon ET) after administration of study drug or until the subject requires rescue medication. Assessments must be made by the Investigator, or designee. Pain will be assessed at time of rescue, but no pain assessments will be completed beyond administration of rescue medication.
- Measurement of vital signs at 15 and 30 minutes and at 1, 1.5, 2, 4, 6, 8, 12, and 24 hours (or upon ET) after administration of study drug.
- Assess respiratory (see section [12.2](#)) and neurological function (see section [12.3](#) and [Appendix A](#)) at 15 and 30 minutes and at 1, 1.5, 2, 4, 6, 8, 12, and 24 hours (or upon ET) after administration of study drug. Assessments must be made by the Investigator, or designee.
- Collection of blood samples for pharmacokinetic assessments at 15 and 30 minutes and at 1, 1.5, 2, 4, 6, 8, 12, and 24 hours (or upon ET) after administration of study drug.
- Record food consumption: capture the date and time of each consumption of food as well as what was consumed eg, DAT, DAT-soft, FFs, CFs, water from 1 hour prior to first dose of study drug administration through EOS/ET.
- Record rescue medication: provide rescue medication on an as needed basis for breakthrough pain (BTP). Rescue medication may include opioid-based patient controlled analgesia (PCA) rescue (but must NOT contain oxycodone or oxymorphone) for as long as the PCA device remains in place per SOC. Oral rescue medications will also be allowed during the study, but also must NOT contain oxycodone or oxymorphone.
- Monitor and document AEs/SAEs throughout the study.
- Update and record concomitant medications (including rescue medications).

Subjects will complete the Single-Dose Phase when they complete the EOS assessments and procedures at 24 hours (or upon ET) following initial study drug administration.

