7.1.6. End-of-Study/Early Termination Assessments and Procedures

At the completion of the single- or multiple-dose phases, EOS/ET assessments and procedures will occur at 24 or 48 hours after initial study drug administration or upon early discontinuation. Each subject will be required to complete all EOS/ET assessments and procedures unless consent/assent, as applicable, has/have been withdrawn. End-of-study assessments will include:

- Collecting AEs/SAEs: all AEs/SAEs that occur during the Screening Phase and thereafter that started after Informed Consent/Assent, as applicable, has/have been signed.
- Performing physical examination: a comprehensive physical examination, excluding height and weight, to assess the subject's overall health and physical status. Record only abnormalities observed during the examination.
- Measuring vital signs: temperature, heart rate (beats per minute), respiratory rate (breaths per minute), and blood pressure (systolic and diastolic blood pressure, mmHg).
- Collecting a blood sample for pharmacokinetic assessments
- Collecting a blood sample for clinical laboratory tests: clinical laboratory tests as part of SOC will be acceptable.
 - Chemistry panels may include analysis of the analytes listed in section 12.5.3.
 - Hematology panels may include analysis of the analytes listed in section 12.5.4.
- Assessing respiratory and neurological function (see sections 12.2 and 12.3 and Appendix A). Assessments must be made by the Investigator, or designee.
- Updating and recording concomitant medications (including rescue medications).
- Assessing and recording current pain intensity (prior to giving rescue or further analgesics according to SOC) using an age-appropriate pain assessment instrument (FPS-R for ages 6 to ≤12; FLACC for ages 2 to <6 [see Appendix C and Appendix D, respectively]).
- Converting subjects to a discharge marketed opioid, if required.
- Scheduling the 14-day follow-up telephone call: assessment to include ongoing or new AEs, SAEs, and associated concomitant medications.

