12.1.1. Monitoring

Throughout the study, AEs will be documented on the source document and on the appropriate page of the eCRF whether or not considered treatment-related including any new signs, symptoms, injury or illness, and increased severity of previously existing signs, symptoms, injury, or illness. Conditions existing prior to signing informed consent/assent will be recorded as part of the subject's medical history. The Investigator is responsible for assessing the relationship of AEs to the study drug; relationship will be classified as not related, unlikely related, possibly related, or probably related (see section 12.1.2 for definitions). Any lab result obtained as part of SOC will be reviewed by the Investigator; any clinically meaningful lab value abnormality will be recorded as an AE at the discretion of the Investigator.

All AEs will be collected by the Investigator through 14 days after the last dose of study drug; this includes any AEs that are ongoing at the completion/termination of the study, and any AEs that start after the last dose of study drug, but before the 14-day post-study period.

Any SAE, including death resulting from any cause, which occurs to any subject participating in this study or within 14 days following cessation of the study treatment or premature discontinuation from the study whether or not related to the investigational product, must be reported via facsimile or telephone within 24 hours of first being advised of the SAE. Follow-up information collected for any initial report of an SAE must be reported to the Sponsor within 24 hours of receipt by the Investigator. In the event discussion is necessary regarding treatment of the subject, the Investigator should call the Medical Monitor. SAEs will be followed until resolution, stabilization or until follow-up is no longer possible.

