13.2. Analysis Populations

The safety population will include all subjects who take at least 1 dose of study drug. All safety analyses will be performed using this population. The effectiveness population will include all subjects who take at least 1 dose of study drug and who have completed at least 1 post dose pain intensity assessment. All effectiveness analyses will be performed using this population. All subjects who receive study drug as planned and have sufficient plasma concentration data to facilitate the calculation of pharmacokinetic variables will be evaluable for pharmacokinetic analysis. Final subject evaluability will be determined prior to locking the database.

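### In the Single-Dose Phase, loss of the sampling line ends the child's whole participation, although the only dose has been given and the remaining timed bedside assessments need no line (minor)

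*Combined protocol and SAP*

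**What the plan says.** Section 12.4.1 (Blood Sample Collections) allows a lost line to be replaced only if clinical management calls for it. Failing that, the child's "participation in the study will be early terminated". This ends participation in the study, not just PK sampling, and there is no exception for the Single-Dose Phase.

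The Single-Dose schedule in Section 7.1.4 calls for "Measurement of vital signs at 15 and 30 minutes and at 1, 1.5, 2, 4, 6, 8, 12, and 24 hours", or upon ET. Respiratory, neurological and pain assessments follow the same ten times, with pain scored only until rescue. Sections 12.2, 12.3 and 11.1 describe the methods: pulse oximetry and observation of breathing, a sedation scale, and FPS-R or FLACC.

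For rescue in this phase, the note to Figure 1 in Section 7 takes a narrower approach: "if rescue is needed, all study procedures (including PK) will continue except collection of pain scores". PK stops only if the rescue drug is oxycodone or oxymorphone.

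Section 6.1 states that the primary objective "is to characterize the effectiveness, safety, and tolerability of oxymorphone HCl immediate-release oral liquid"; PK is a secondary objective in Section 6.2. Section 13.2 defines PK evaluability on its own terms: subjects who received drug as planned and "have sufficient plasma concentration data to facilitate the calculation of pharmacokinetic variables will be evaluable for pharmacokinetic analysis". The safety population needs only one dose, and the effectiveness population adds one post-dose pain score.

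On what survives termination, Section 7.1.6 says "Each subject will be required to complete all EOS/ET assessments and procedures" unless consent or assent is withdrawn, and Section 12.1.1 says "All AEs will be collected by the Investigator through 14 days after the last dose of study drug".

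**The concern.** The rule lets a logistical failure in a secondary-objective measurement stop the collection of primary-objective data. In a single-dose design the usual reasons for ending participation do not apply once the dose is swallowed: there is no further exposure to prevent, and terminating the child does not produce the missing blood samples. What it does stop is the series of timed bedside readings.

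Those readings matter because, under Section 7, the IDMC reviews individual and aggregate effectiveness, safety and tolerability data before each escalation, from cohorts of 6 per age group. Section 13.5 summarizes vital signs and respiratory and neurological assessments by time point, so one ET set taken early does not stand in for the later scheduled times. Section 13.7 allows no imputation of these data. AUC_E, defined in the abbreviations list as the PID area divided by the time covered, would describe a shorter window for such a child.

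**Working it through.** The plan gives no figure on this point, so there is none to reproduce. The check is a count of scheduled assessments.

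**Inputs**
- Post-dose times (Section 7.1.4, Table 3): 0.25, 0.5, 1, 1.5, 2, 4, 6, 8, 12, 24 h, which is 10 sets.
- Sets recovered at termination (Section 7.1.6): 1.
- Cohort size (Section 13.1): 6 per age group and dose.
- Line-loss rate: not given.

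**Per child.** Net loss = (scheduled times after the line is lost) − 1 ET set.

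| Line lost | Times remaining | Net sets lost of 10 |
|---|---|---|
| before 0.25 h | 10 | 10 − 1 = 9 |
| 0.25 to 0.5 h | 9 | 9 − 1 = 8 |
| 0.5 to 1 h | 8 | 8 − 1 = 7 |
| 1 to 1.5 h | 7 | 7 − 1 = 6 |
| 1.5 to 2 h | 6 | 6 − 1 = 5 |
| 2 to 4 h | 5 | 5 − 1 = 4 |
| 4 to 6 h | 4 | 4 − 1 = 3 |
| 6 to 8 h | 3 | 3 − 1 = 2 |
| 8 to 12 h | 2 | 2 − 1 = 1 |
| after 12 h | 1 | 1 − 1 = 0 |

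This applies to vital-sign, respiratory and neurological assessments. Pain scores are lost only in a child not yet rescued. The Synopsis frames effectiveness as "assessment of current pain intensity will be obtained using the FPS-R for 12 hours (Single-Dose Phase"), and Section 9.3 allows standard-of-care analgesia after that. Counting only the 9 pain times up to 12 h, the net loss is 4 − 1 = 3 for a line lost between 2 and 4 h, 3 − 1 = 2 between 4 and 6 h, 2 − 1 = 1 between 6 and 8 h, and 1 − 1 = 0 between 8 and 12 h.

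**Per cohort, only if the child is not replaced.** Scheduled readings per assessment type: 6 × 10 = 60. The number of children affected is an assumption.

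| Children losing the line (assumed) | before 0.25 h | 2 to 4 h | 6 to 8 h | 8 to 12 h | after 12 h |
|---|---|---|---|---|---|
| 0 of 6 | 0% | 0% | 0% | 0% | 0% |
| 1 of 6 | 9/60 = 15.0% | 4/60 = 6.7% | 2/60 = 3.3% | 1/60 = 1.7% | 0% |
| 2 of 6 (same window) | 18/60 = 30.0% | 8/60 = 13.3% | 4/60 = 6.7% | 2/60 = 3.3% | 0% |

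If the child is replaced, the cohort has its 60 scheduled readings plus the partial set, and these percentages do not apply.

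**Line loss set beside rescue.** After rescue, the measure that is compromised (pain) stops and the rest goes on. After line loss, the measure that is compromised is PK, yet everything stops. Because Section 13.2 already keeps PK evaluability apart from the other two populations, no analysis set would need redefining if the bedside assessments continued.

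**The case against.** The case for the rule as written is that PK is woven through this study. Section 13.5 bases safety and tolerability partly on PK, a line is an entry condition (inclusion criterion 11), and the only numerical justification of sample size in Section 13.1 is the precision of clearance and volume. On that view, ending participation when sampling becomes impossible is deliberate. It may well be, but the rule gains no PK: the samples are missing whether or not the child stays.

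The rescue comparison is imperfect, since rescue leaves PK usable while line loss removes it. That explains why PK sampling must stop, not why the other assessments should.

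Three further points stand and limit the size of the matter. First, Section 9.2 enrolls to a number of evaluable subjects and Section 7 ties escalation to completion of a cohort of 6, which may imply replacement; a replacement would fill the cohort, though not the first child's own later readings. Second, many of the readings at stake come late: the 8, 12 and 24 h times lie beyond the 4 to 6 h dosing interval used in the Multiple-Dose Phase, and pain scoring may already have stopped for rescue. Third, a child who stays remains under the analgesic limits of Section 9.3 that termination would lift, although rescue remains available.

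**Conclusion.** In the Single-Dose Phase the rule causes a modest, avoidable loss of primary-objective data, between 0 and 9 of 10 scheduled bedside sets per affected child depending on when the line fails. Severity is minor. The result assumes that the line fails after dosing, that it is not replaced for clinical care, and that the ET set is completed.

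Four stronger readings are tempting, and the documents do not support them:
- A reader might infer that the child is lost to safety follow-up or dropped from analysis. The ET set and adverse-event collection to 14 days continue, and Section 13.2 keeps the child in the safety population and, with one post-dose pain score, in the effectiveness population.
- A reader might infer bias in the escalation data. Nothing in the documents links line loss to pain or tolerability, so what can be shown is fewer readings and a shorter AUC_E window.
- A reader might take the cohort percentages as expected losses. They rest on assumed line-loss counts and on no replacement; with no line loss, the effect is nil.
- A reader might extend the point to the Multiple-Dose Phase. There, under Section 7.1.5, assessments after 2 h post-Dose 1 are tied to the remaining doses, and termination does stop further exposure.

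**What to change.** Amend Section 12.4.1 for the Single-Dose Phase so that loss of the line, when it is not replaced for clinical care, ends PK sampling only. Scheduled non-blood assessments then continue to 24 h, with pain scored until rescue as now. The child stays in the safety and effectiveness populations, and PK evaluability is judged under Section 13.2. Whether the child is replaced for PK should be handled as it would be under the present rule, so that the change does not itself alter PK enrollment. Leave the Multiple-Dose Phase unchanged; dosing a child there without a line is a separate safety decision for the sponsor.

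The cost is a short text change and the completion of bedside checks already scheduled in children expected to be inpatients for at least 24 h (inclusion criterion 4). A few children will contribute without a full PK profile, which they would lack in any case, and they stay under the Section 9.3 limits with rescue available.

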
Name of Sponsor/Company: Endo Pharmaceuticals Inc.
Name of Investigational Product: EN3319 Oxymorphone HCl Immediate-Release Oral Liquid
Name of Active Ingredient: Oxymorphone HCl

Pharmacokinetic Analysis: Pharmacokinetic variables (Single-Dose Phase: C_{max}, T_{max}, C_{12}, AUC_{0-t}, AUC_{0-24}, $AUC_{0-\infty}$, λ_n, $t_{1/2}$, CL/F, and V/F; Multiple-Dose Phase: C_{max}, T_{max}, AUC_{0-t}, λ_n, $t_{1/2}$, CL/F, and V/F) will be estimated from the plasma concentration data using standard non-compartmental methods. Actual sample times, rather than scheduled times, will be used in the computation of pharmacokinetic parameters. The definitions and methods of determination for each pharmacokinetic variable are summarized in Table 7.
 
Pharmacokinetic variables (CL/F, V/F, λ_n, and $t_{1/2}$, and dose normalized C_{max}, C_{12}, AUC_{0-24}, AUC_{0-t}, $AUC_{0-\infty}$) will be summarized by age group using N, mean, standard deviation (SD), geometric mean, CV, minimum, median, and maximum following dosing in the Single-Dose Phase and the first and third doses in the Multiple-Dose Phase. In addition, a 2-sided 95% CI will be constructed for both CL/F and V/F. T_{max} will be summarized by age group using median, minimum, and maximum.

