13.6. Pharmacokinetic Analysis

Pharmacokinetic variables (Single-Dose Phase: C_{max} , T_{max} , C_{12} , AUC_{0-t} , AUC_{0-24} , $AUC_{0-\infty}$, λ_n , $t_{1/2}$, CL/F, and V/F; Multiple-Dose Phase: C_{max} , T_{max} , AUC_{0-t} , λ_n , $t_{1/2}$, CL/F, and V/F) will be estimated from the plasma concentration data using standard non-compartmental methods. Actual sample times, rather than scheduled times, will be used in the computation of pharmacokinetic parameters. Plasma concentrations below limit of quantification (BLQ) will be set to zero in the computation of mean concentration values; however, BLQ concentrations between 2 non-BLQ concentrations will be set to missing. For the computation of pharmacokinetic variables, the BLQ concentrations prior to the first measurable concentration

will be set to zero and other BLQ concentrations will be set to missing. The definitions and methods of determination for each pharmacokinetic variable are summarized in [Table 7](#).

Pharmacokinetic variables (CL/F , V/F , λ_n , and $t_{1/2}$, and dose normalized C_{max} , C_{12} , AUC_{0-24} , AUC_{0-t} , $AUC_{0-\infty}$) will be summarized by age group using N, mean, standard deviation (SD), geometric mean, CV, minimum, median, and maximum following dosing in the Single-Dose Phase and the first and third doses in the Multiple-Dose Phase. In addition, a 2-sided 95% CI will be constructed for both CL/F and V/F . T_{max} will be summarized by age group using median, minimum, and maximum.

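### Table 7 prints the half-life formula inverted (λ_n/ln 2 instead of ln 2/λ_n); secondarily, the Multiple-Dose PK summaries do not match the sampling schedule

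*Combined protocol and SAP*

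**What the plan says.** **Half-life.** In Table 7 (Section 12.4.1) λ_n is "calculated as the negative slope of the ln-linear portion of the terminal plasma concentration-time curve". The next row is "Terminal half-life, calculated as $\lambda_n/(\ln 2" (closing bracket omitted here). The synopsis gives Table 7 governing status: "The definitions and methods of determination for each pharmacokinetic variable are summarized in Table 7". Section 13.6 repeats this. Half-life is a listed variable in both phases and is summarised by age group.

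**Multiple-Dose summaries.** The synopsis and Section 13.6 plan PK summaries after the first and third doses of the Multiple-Dose Phase. Sections 7.1.5 and 12.4.1 schedule samples at 0.5, 1, 1.5 and 2 h after Dose 1, one pre-dose sample at each of Doses 2 to 7, and samples at 0.5, 1, 1.5 and 2 h after Dose 7.

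**Multiple-Dose variables.** The list in Section 12.4.1 stops at clearance: "and CL/F; see [Table 7](#) for definitions". The synopsis list continues to "CL/F, and V/F. Safety and Tolerability", and Section 13.6 has "CL/F, and V/F) will be estimated from the plasma concentration data using standard non-compartmental methods".

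**Sample number.** Table 4, footnote f, caps PK samples at 15. Section 7.1.6 also lists a PK blood sample at end of study or early termination, without limiting it to one phase.

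**The concern.** The slope of ln concentration on time has the unit 1/time. Dividing it by the pure number ln 2 leaves 1/time, which cannot be a half-life. If the analysis is programmed from Table 7, every value in the half-life column is wrong in size and unit, and a child who eliminates the drug faster shows the larger number. Half-life is part of the PK profile named as a secondary objective in Section 6.2, and the same section seeks dosing recommendations by the end of the study.

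The second problem is different in kind. Software will not repair it, because a summary after the third dose calls for concentrations that the schedule does not collect.

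**Working it through.** **1. Half-life from the plan's own definition.** In the terminal phase C(t) = C0 × exp(−λ_n × t). Setting C(t + t½)/C(t) = 0.5 gives exp(−λ_n × t½) = 0.5, hence t½ = (ln 2)/λ_n. The printed rule gives λ_n/(ln 2) = 1/t½.

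**2. Could λ_n mean something else?** Two other Table 7 rows rule this out. AUC0-∞ adds Ct/λ_n to an area, and V/F is Dose/(AUC0-∞ × λ_n). Both have correct units only if λ_n is 1/time. Both rows are right as printed.

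**3. Size.** The documents give no half-life, so these true values are assumed:

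| True t½ (h) | λ_n (per h) | Correct rule (h) | Printed rule (per h) |
|---|---|---|---|
| 1 | 0.6931 | 1 | 1 |
| 2 | 0.3466 | 2 | 0.5 |
| 4 | 0.1733 | 4 | 0.25 |
| 8 | 0.0866 | 8 | 0.125 |
| 12 | 0.0578 | 12 | 0.083 |

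The numbers agree only at exactly 1 h. With a true half-life of 8 h, reading 0.125 as hours leaves exp(−0.0866 × 0.125) = 98.9% of the concentration, not 50%. No fold error is quoted, because it would change with the time unit.

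**4. Ordering of groups.** Reciprocals reverse the order of individual values. The geometric mean of 1/t½ is 1 divided by the geometric mean of t½, so geometric means reverse too. Arithmetic means need not. Take half-lives of 1 and 9 h (mean 5) against 4 and 4 h (mean 4). The printed rule gives (1 + 1/9)/2 = 0.56 against 0.25, and the order is unchanged.

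**5. What each Multiple-Dose interval contains.** The dosing interval is 4 to 6 h.

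| Dose | Samples in the interval | Consequence |
|---|---|---|
| 1 | 0, 0.5, 1, 1.5, 2 h, then pre-Dose 2 | Serial profile |
| 3 | Pre-Dose 3, then pre-Dose 4 | One post-dose value: no λ_n, half-life or V/F |
| 7 | Pre-Dose 7, then 0.5, 1, 1.5, 2 h | Nothing after 2 h; no pre-Dose 8 sample |

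After Dose 7 the unsampled share of the interval is (4 − 2)/4 = 50% to (6 − 2)/6 = 67%. Table 7 takes steady-state CL/F as Dose/AUC(0-τ), which needs concentrations to the end of the interval.

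**6. Sample count.** Section 12.4.1 gives 1 + 4 + 6 + 4 = 15, exactly the cap. A completer who also has the end-of-study sample of Section 7.1.6 would have 16.

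**The case against.** The best defence is that this is a typographical inversion in one cell. Section 13.6 calls for standard non-compartmental methods, and the usual software computes half-life correctly whatever Table 7 says. λ_n is summarised next to half-life, so a literal implementation would give a half-life equal to λ_n × 1/0.6931, about 1.44 × λ_n, in every subject. That is easy to notice, and subject-level values can be recovered by inversion. Half-life has only descriptive summaries. All of this stands, and it limits the impact. It does not make the cell correct, because the synopsis and Section 13.6 name Table 7 as the source of the methods.

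A reader might infer that exposure, clearance or volume results are also wrong, or that cohort escalation is affected. The documents do not support this. AUC0-∞ and V/F use λ_n itself, CL/F uses AUC, and no escalation rule refers to half-life. A reader might also infer that every comparison of age groups would reverse; step 4 shows that arithmetic means need not.

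On V/F, Table 7's only form starts "Apparent volume of distribution, calculated as Dose" and uses AUC0-∞, which is on neither Multiple-Dose list. A reader might conclude that Multiple-Dose V/F must be dropped. That is a preference: the single-dose form is valid at Dose 1, and a repeat-dose formula could be added.

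**Conclusion.** The half-life formula is wrong as written and should be corrected. The result follows from Table 7's own definition of λ_n; only the illustrative half-lives are assumed. Followed literally, every reported half-life is the reciprocal of the true one, in 1/time. The practical risk is small, for the reasons that stand above.

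The secondary inconsistencies are also real. Dose 3 values of λ_n, half-life and V/F cannot be derived from the Dose 3 interval. Replacing the third dose by the seventh in the text would not settle the matter, since λ_n, half-life and CL/F by Dose/AUC(0-τ) are doubtful from samples that end at 2 h. Doubtful is the right word rather than impossible: some analysts would let the pre-Dose 7 value stand for the end of the interval at steady state, but the plan states no such rule. Whether Multiple-Dose V/F is planned, and whether a completer gives 15 or 16 PK samples, the documents leave unclear.

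**What to change.** **Main:** change the Table 7 cell to t½ = (ln 2)/λ_n. This is one cell, with no effect on data or on any other formula.

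**Secondary:**
- Reconcile the doses named for the Multiple-Dose summaries (synopsis, Section 13.6) with the sampling in Sections 7.1.5 and 12.4.1.
- For each dose, list only the variables that its samples can support. If λ_n, half-life or CL/F is kept for Dose 7, state how concentrations beyond 2 h are handled.
- Make the Multiple-Dose variable lists in the synopsis, Section 12.4.1 and Section 13.6 agree on V/F. If it stays, name the dose and the formula.
- Reconcile the end-of-study PK sample in Section 7.1.6 with the schedule and with the 15-sample cap in Table 4, footnote f.

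These are text changes as long as reporting is limited to what the present samples support. Adding samples would cost more, because the scheduled 15 already fill the cap.
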